7.3.1.2 Safety Oversight by the Dose Escalation Steering Committee

A DESC will be responsible for safety monitoring and overall supervision of the study. Membership of the DESC will include:

- Medical monitor(s)/Pharmacovigilance representative(s) (Sponsor and/or designee)
- Investigator(s) from each participating site
- Biostatistician(s)
- Ad-hoc members (e.g., project manager, study coordinators, regulatory representatives, etc.)

In general, the DESC will make any substantial decisions regarding the conduct of the study, such as:

- Monitor the safety of the study and review its progress at monthly intervals or more frequent intervals as required.
- In accordance with the CRM ([Appendix 13.5](#)), determine dose levels to be administered and the MTD based on assessment of safety findings and determination of DLTs.
- While the DESC cannot dictate dose level(s) higher than those prescribed by the CRM, the medical judgment of the DESC will supersede the statistical parameters of the CRM.
- Approve any amendments or administrative changes to the protocol, when required.

Each DESC meeting and the decisions made will be documented in writing and provided to all participating DESC members and Investigators. Meeting documents may be submitted to IRBs/IECs or competent authorities according to institutional or local requirements.

Dose escalation will be conducted according to a CRM, as described in [Appendix 13.5](#).

The first patient at each new dose will be monitored for any AEs for 7 days before proceeding with dosing for second patient.

During dose escalation, the DESC may expand enrollment at doses below the current dose level being evaluated as part of the dose escalation process. Patients may only be added to the lower doses provided there is at least 1 patient with an efficacy evaluation showing stable disease. No more than 10 patients in total can be treated at any dose level unless at least 3 of the 10 patients have documented partial response or better using the 2014 Lugano Classification criteria² or other appropriate measures of response ([Appendix 13.3](#)).

The DESC will be maintained during Part 2 (expansion) of the study to continue to monitor and evaluate patient safety.

7.3.2 Adverse Events

7.3.2.1 Definitions of Adverse Events

The Investigator is responsible for reporting all AEs that are observed or reported during the study, regardless of their relationship to study drug or their clinical significance.

An AE is defined as any untoward medical occurrence in a patient enrolled into this study regardless of its causal relationship to study drug. Patients will be instructed to contact the Investigator at any time after the patient signs the ICF if any symptoms develop.

A treatment-emergent AE (TEAE) is defined as any event not present before exposure to study drug or any event already present that worsens in either intensity or frequency after exposure to study drug.

A serious adverse event (SAE) is defined as any event that results in death, is immediately life threatening, requires inpatient hospitalization or prolongation of existing hospitalization, results in persistent or significant disability/incapacity, or is a congenital anomaly/birth defect. Hospitalization for elective procedures or for protocol compliance is not considered an SAE.

Important medical events that may not result in death, be life threatening, or require hospitalization may be considered SAEs when, based upon appropriate medical judgment, they may jeopardize the patient or may require medical or surgical intervention to prevent 1 of the outcomes listed in this definition. Examples of such medical events include allergic bronchospasm requiring intensive treatment in an emergency room or at home, blood dyscrasias or convulsions that do not result in inpatient hospitalization, or the development of drug dependency or drug abuse.

7.3.2.2 Eliciting and Documenting Adverse Events

All AEs will be assessed from the time the patient signs the ICF until 84 days (12 weeks) after the last dose of study drug, or initiation of new anticancer treatment.

Any SAEs that occur > 84 days (12 weeks) after the last dose of study drug do not need to be reported unless the Investigator considers the event to be related to study drug.

At every study visit, patients will be asked a standard non-leading question to elicit any medically related changes in their well-being. They will also be asked if they have been hospitalized, had any accidents, used any new medications, or changed concomitant medication regimens (both prescription and over-the-counter medications).

In addition to patient observations, AEs will be documented from any data collected on the AE page of the eCRF (e.g., clinically significant changes in laboratory values, physical examination, ECG changes, etc.) or identified from review of other documents that are relevant to patient safety.

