5.1.6 Long-term Follow-up

Patients who discontinue treatment for any reason other than objective disease progression will continue to be followed with scans approximately every 12 weeks from the last tumor assessment until disease progression, or initiation of new anticancer treatment. If a patient discontinues treatment for a hematopoietic stem cell transplant, the frequency of imaging will be as per the transplant center standard of care.

After documentation of disease progression or start of new anticancer treatment, patients will be contacted by telephone approximately every 12 weeks for up to 12 months after the last dose of study drug to collect survival information.

Blood Sample Collection and Adverse Event Monitoring During Long-Term Follow-up

For all patients, PK and ADA blood sample collection will be performed 12 weeks (\pm 1 week) following the last dose of ADCT-301, unless a new anticancer treatment has been initiated.

Patients who test positive for ADAs may be requested to supply additional ADA samples.

For all patients, collection of AEs and SAEs will continue for 12 weeks after the last dose of study drug or initiation of new anticancer treatment (see [Section 7.3.2.2](#)).

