6.5 Study Stopping Rules

The study will be paused if any of the following circumstances occur:

- \geq 30% of patients experience a specific Grade 4 or higher non-hematologic treatment-emergent AE.
- if any patient in Part 1 or Part 2 experiences a CTCAE Grade 5 AE, or 2 non-hematologic CTCAE Grade 4 AEs that are not attributable to the underlying disease, and for which relationship to ADCT-301 cannot be ruled out, within 30 days of their last dose of ADCT-301.

Furthermore, the Sponsor will notify regulatory agencies within 48 hours of being made aware of any new confirmed cases of GBS/polyradiculopathy to discuss, if appropriate, and determine whether or not the benefit-risk ratio has changed and dosing of additional patients and/or dosing of ongoing patients must be stopped. IRBs/IECs will be informed about the outcome of the assessment as appropriate.

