8.6.2 Safety Analyses

8.6.2.1 Analyses of Adverse Events

An AE will be considered to be a TEAE if it begins or worsens on or after first dose date and before last dose date until 84 days (12 weeks). Planned summaries of TEAEs are detailed in the statistical analysis plan and will include:

- All TEAEs.
- All serious TEAEs.
- All treatment-related TEAEs.
- All treatment-related serious TEAEs.
- All TEAEs resulting in study drug discontinuation.
- All DLTs.
- Other AE analyses of interest will be specified in the SAP.

The incidence of deaths and the primary cause of death will be summarized.

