- 22 Patients to receive ADCT-301 intravenously over 1 hours (\pm 15 minutes). If ADCT-301 is well tolerated after the first cycle, the infusion duration may be shortened to a 30-minute intravenous infusion for subsequent cycles at the Investigator's discretion. The IP administration window is \pm 15 minutes.
- 23 Dexamethasone prophylaxis (4 mg BID on Day -1, Day 1, and Day 2) should be administered, unless contraindicated. If Grade 2 or higher infusion-related hypersensitivity reactions are observed in a patient at any time during the study, this patient must receive prophylactic treatment with all subsequent dosing to reduce the risk of hypersensitivity reaction. Prophylaxis for hypersensitivity will supersede stipulations on dexamethasone prophylaxis
- 24 For all patients, collection of AEs and SAEs will continue for 12 weeks (84 days) after the last dose of study drug or initiation of new anticancer treatment. Any SAEs that occur more than 84 days after the last dose of study drug do not need to be reported unless the Investigator considers the event to be related to study drug.
- 25 To include prescription or over-the-counter medication, herbal or naturopathic products within the 14 days prior to Day 1, throughout the study, and for 30 days after last dose of study drug.
- 26 After documentation of disease progression or start of new anti-cancer treatment, patients will be contacted by telephone approximately every 12 weeks for up to 12 months after the last dose of study drug to collect survival information.
- 27 Information on anti-cancer treatment initiated after discontinuation of ADCT-301 to be recorded in the eCRF.

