### 4.8.2 Adverse Events, Serious Adverse Events, and Deaths

#### 4.8.2.1 Analyses of adverse events

The primary focus of adverse event reporting will be on TEAEs. An adverse event (AE) will be considered to be a TEAE if it begins or worsens on or after first dose date and until 84 days (12 weeks) after the last dose date, or start of a new anticancer therapy/procedure, whichever comes earlier.

An AE occurring before the first dose or more than 84 days (12 weeks) after last dose date or after the start of a new anticancer therapy/procedure will not be included in TEAE displays, but will be listed as non-TEAEs.

If an AE date/time of onset (occurrence, worsening, or becoming serious) is incomplete, an imputation algorithm will be used to classify the AE as pre-treatment, TEAE, or post-treatment. The algorithm for imputing date/time of onset will be conservative and will classify an AE as a treatment-emergent unless there is definitive information to determine it is a non-TEAE (pre- or post-treatment).

Details on classification of AEs with missing or partial onset dates are provided in Section 6.

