#### **4.8.2.2 Deaths**

The following deaths summaries will be generated on the safety analysis set.

- Number (%) of patients who died during the study and reasons for death
- Number (%) of patients who died within 30 days after last dose of study drug except deaths occurred after taking any subsequent anticancer therapy/procedure and reasons for death

All deaths will be listed.

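### The protocol does not say whether new anticancer treatment ends AE/SAE collection before Day 84; if it does, events counted by the 30-day pause rule and related SAEs before Day 84 may be missed or delayed in early switchers

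*Protocol*

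**What the plan says.** **Collection window.** Protocol 7.3.2.2 has AEs assessed from consent "until 84 days (12 weeks) after the last dose of study drug, or initiation of new anticancer treatment". Protocol 5.1.6 says that "collection of AEs and SAEs will continue for 12 weeks after the last dose of study drug or initiation of new anticancer treatment", and footnote 24 of the schedule (13.1.1) repeats this. None of the three says whether the earlier or the later limit applies. Protocol 5.1.5 gives the 84-day limit alone.

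**Late SAEs.** Section 7.3.2.2 adds a rule for SAEs later than Day 84: those that fall beyond that limit "after the last dose of study drug do not need to be reported unless the Investigator considers the event to be related to study drug". New therapy is not mentioned.

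**Pause rule.** Protocol 6.5 pauses the study for one Grade 5 AE, or two non-hematologic Grade 4 AEs, that the lymphoma does not account for and "for which relationship to ADCT-301 cannot be ruled out, within 30 days of their last dose of ADCT-301". It has no exemption after new therapy. The same section requires notice to regulators within 48 hours of the sponsor learning of a confirmed GBS/polyradiculopathy case, also without such a limit.

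**Analysis.** Protocol 8.6.2.1 begins "An AE will be considered to be a TEAE if it begins or worsens on or after first dose date" and runs the window to 84 days, with no cut at new therapy. SAP 4.8.2.1 ends it at "until 84 days (12 weeks) after the last dose date, or start of a new anticancer therapy/procedure, whichever comes earlier". SAP 4.8.2.2 summarises patients who "died within 30 days after last dose of study drug except deaths occurred after taking any subsequent anticancer therapy/procedure". SAP 3.3, which records departures from the protocol's statistical section, lists only the efficacy analysis set.

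**The concern.** Safety and tolerability are primary objectives in both parts, and a single Grade 5 event can trigger the pause. A rule with a 30-day window needs collection that reliably lasts 30 days. If collection ends when new treatment starts, a patient who switches sooner is no longer actively asked about events that the rule still counts.

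The related-SAE clause raises a second problem. It speaks only of events after Day 84. A related SAE on Day 90 is clearly reportable, while one on Day 50 in a patient who switched on Day 25 is not clearly covered. Late neurological events are exposed in the same way. The Level 1 GBS definition (Protocol 13.6) allows up to 28 days from onset to nadir and then requires a plateau, so a case can be confirmed well after its first signs.

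The third problem is one of reporting. The SAP narrows two safety summaries relative to the protocol, and a reader of the study report would not learn this from SAP 3.3.

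**Working it through.** The plan gives no figure for this point beyond 12 weeks = 12 × 7 = 84 days, which agrees. The check compares readings of the text and then counts days.

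**1. Readings of the collection clause.**
- *Earlier of the two limits.* This is the SAP's choice for TEAEs. Collection can end at the switch.
- *Later of the two.* Collection lasts at least to Day 84. But it would also run routinely past Day 84 in anyone who switches later, which sits badly with the next sentence of 7.3.2.2 limiting later SAE reporting to related events.
- *Twelve weeks after either event.* The wording of 5.1.6 and footnote 24 allows this. Collection again lasts at least to Day 84.

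The gap exists only under the first reading. That reading fits the late-SAE sentence best, but the protocol does not state it.

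**2. Is a switch inside 30 days feasible?** Protocol 5.1.2 schedules disease assessment within 6 days before Day 1 of Cycles 3 and 5. With 21-day cycles, that is as early as 21 − 6 = Day 15 after the previous dose. A switch from about Day 15 is therefore possible. The documents give no switch rate.

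**3. Days without active collection, earlier-of reading.** For a switch on day *s* after the last dose:
- pause-rule days uncovered = max(0, 30 − *s*)
- collection days uncovered = max(0, 84 − *s*)

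| Switch day (assumed) | Of 30 days | Of 84 days |
|---|---|---|
| 15 | 15 (50%) | 69 (82%) |
| 21 | 9 (30%) | 63 (75%) |
| 28 | 2 (7%) | 56 (67%) |
| 30 | 0 | 54 (64%) |

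**4. Illustration for Grade 5 events.** None of these rates is in the documents. Suppose that a share *w* = 10% to 30% of patients switch early, the related Grade 5 risk over 30 days is *r* = 1% to 3% in every patient, events fall evenly over the 30 days, and the uncovered share is *g* = 0.3 (Day 21) to 0.5 (Day 15). The chance that at least one such death falls in uncovered days is 1 − (1 − *w r g*)^*n*.
- *n* = 60 (Part 2): 1 − (1 − 0.0003)^60 = 2% to 1 − (1 − 0.0045)^60 = 24%.
- *n* = 140 (both parts): 4% to 47%, from the same two products.

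This is the chance that an event falls where nobody is scheduled to ask. The chance that it is never reported is smaller.

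**5. Protocol against SAP.** Protocol 8.6.2.1 has no new-therapy cut. SAP 4.8.2.1 and the 30-day item in 4.8.2.2 have one, and SAP 3.3 is silent. This difference does not depend on how step 1 is resolved.

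**The case against.** A reader might infer that drug-related deaths, Grade 4 events and GBS in early switchers simply go uncollected. The documents do not support that, for these reasons:
- The protocol never says that the earlier limit governs.
- Section 7.3.2.1 makes the investigator responsible for all AEs observed or reported during the study, and participation runs through follow-up (5.2).
- Section 7.3.2.3 requires any SAE to be reported within 24 hours of site personnel learning of it. Grade 5 events, and Grade 4 events that are immediately life-threatening, are SAEs.
- The end-of-treatment visit, with neurological examination and AE collection, is placed before new treatment (5.1.5). An AE that causes discontinuation is followed to resolution (5.2.2).
- SAP 4.8.2.2 tabulates all on-study deaths with reasons and lists every death. SAP 4.8.2.1 lists AEs after new therapy as non-TEAEs.
- The late related-SAE rule itself works. The unclear stretch lies only between the switch and Day 84, and releasing only SAEs after Day 84 can be read as implying that earlier ones stay reportable.

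These points stand and reduce the gap, but they do not close it. The general duties act on what the site happens to learn, whereas 7.3.2.2 is the specific rule on when AEs are assessed. Sections 5.1.6 and footnote 24 name SAEs in the limiting clause. The contact that remains after a switch is a call about every 12 weeks for survival, which is too slow for a 30-day rule and is not designed to record grade or relatedness. Protocol 4.1 can even be read as ending survival follow-up at new therapy. The SAP can list only what was recorded.

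Truncating TEAE tables at new therapy is a defensible way to limit confounding. The objection is to the undeclared change and the lack of an untruncated companion.

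**Conclusion.** The passages do not fit together and need to be reconciled. On the earlier-of reading, pause-rule events and late neurological events in patients who switch early may be missed or delayed, and related SAEs between the switch and Day 84 have no explicit rule. For switches on Day 15 to Day 28, 15 to 2 of the 30 pause-rule days lack active collection; from Day 30, none do. Most exposed are non-serious, non-hematologic Grade 4 events and any event the site does not hear of.

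The size rests on assumed switch days and on one reading of an ambiguous clause. A reader might also infer that TEAE and early-death rates are biased downward, most at dose levels where patients leave soonest. The documents give no switch rates by dose and do not support that statement. The protocol/SAP difference in the TEAE window and the 30-day death summary is plain from the text and needs no assumption.

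**What to change.** **Protocol.** Reconcile 5.1.5, 5.1.6, 6.5, 7.3.2.2, footnote 24 and 8.6.2.1 by stating which limit governs. Then:
- Make SAEs considered related reportable at any time after the last dose, whether or not new therapy has started.
- Collect every event type that the pause rule counts (Grade 5 and non-hematologic Grade 4, serious or not) through Day 30 regardless of new therapy, with a contact at about Day 30 for patients who switch earlier. The 12-weekly survival calls cannot serve this purpose.
- Collect SAEs, deaths and GBS/polyradiculopathy to Day 84 regardless of new therapy, flagged by the new-therapy start date, which is already to be collected (footnote 27; SAP 4.7.3).

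**SAP.** Keep the truncated tables. Add supplementary summaries of TEAEs to Day 84 and deaths to Day 30 without the new-therapy cut, and declare the difference from Protocol 8.6.2.1 in SAP 3.3.

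**Cost.** Wording changes in both documents, one extra call for each early switcher, SAE follow-up to Day 84 in those patients, and a few more tables. Some added events will be confounded by the new therapy; the flag lets them be shown separately.

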7.3.2.3 Reporting Adverse Events

All AEs reported or observed during the study will be recorded on the AE page of the eCRF. Information to be collected includes drug treatment, dose, event terminology, date of onset, CTCAE Version 4.0 assessment of severity and relationship to study drug, date of resolution of the event, seriousness, any required treatment or evaluations, and outcome. With the exception of disease progression, AEs resulting from concurrent illnesses, reactions to concurrent illnesses, and reactions to concurrent medications also must be reported. All AEs will be followed to adequate resolution. CTCAE Version 4.0 will be used to grade all AEs. The CTCAE includes 5 grades (1 to 5), with Grade 5 being death.

Any AE that meets SAE criteria ([Section 7.3.2.1](#)) must be reported to the contract research organization (CRO) immediately (i.e., within 24 hours after the time site personnel first learn about the event). The following contact information is to be used for SAE reporting:

[REDACTED]

7.3.2.4 Assessment of Severity

Adverse events are graded according to CTCAE Version 4.0. For events not included in the CTCAE criteria, the severity of the AE is graded on a scale of 1 to 5 as follows:

| | |
|----|--|
| 1: | Mild; asymptomatic or mild symptoms; clinical or diagnostic observations only; intervention not indicated |
| 2: | Moderate; minimal, local or noninvasive intervention indicated; limiting age-appropriate instrumental ADL ^a |
| 3: | Severe or medically significant but not immediately life threatening; hospitalization or prolongation of hospitalization indicated; disabling; limiting self-care ADL ^b |
| 4: | Life-threatening consequences; urgent intervention indicated |
| 5: | Death related to adverse event |

a Instrumental activities of daily living (ADL) refer to preparing meals, shopping for groceries or clothes, using the telephone, managing money, etc.

b Self-care ADL refer to bathing, dressing and undressing, feeding self, using the toilet, taking medications, and not bedridden.

Changes in the severity of an AE should be documented to allow an assessment of the duration of the event at each level of intensity to be performed. Adverse events characterized as intermittent do not require documentation of onset and duration of each episode.

7.3.2.5 Assessment of Causality

The Investigator's assessment of an AE's relationship to study drug is part of the documentation process, but it is not a factor in determining what is or is not reported in the eCRF. All adverse events, regardless of assessment of causality, are reported in the eCRF.

All SAEs considered at least possibly related to the study drug will be considered unexpected; and therefore, reported as Suspected Unexpected Serious Adverse Reactions (SUSARs).

7.3.2.6 Follow-up of Patients Reporting Adverse Events

All AEs must be reported in detail on the appropriate page of the eCRF and followed to satisfactory resolution, until the Investigator deems the event to be chronic or not clinically significant, or until the patient is considered to be stable.

7.3.3 Pregnancy

Any pregnancy that occurs during study participation must be reported using a clinical study Pregnancy Report Form. To ensure patient safety, each pregnancy must be reported as described for reported AEs in [Section 7.3.2.3](#), upon learning of its occurrence. The pregnancy must be followed to determine outcome (including spontaneous miscarriage, elective termination, normal birth, or congenital abnormality) and status of mother and child, even if the patient was discontinued from the study. The outcome of the pregnancy will be reported on the Pregnancy Outcome Form. Spontaneous miscarriages must be reported as an SAE.

Any SAE occurring in association with a pregnancy brought to the Investigator's attention after the patient has completed the study and considered by the Investigator as possibly related to the study treatment must be promptly reported ([Section 7.3.2.3](#)).

